4.6.2 Study Treatment Discontinuation

Study treatment should be permanently discontinued in patients who experience any of the following:

- Anaphylaxis, acute respiratory distress, or Grade 4 IRR
 - If a Grade 3 IRR is recurrent during the second and subsequent cycles, study treatment may be discontinued at the discretion of the investigator, following an individual benefit-risk assessment.
- Life-threatening adverse event
- Grade ≥ 3 non-immune-mediated adverse event that is considered to be related to study treatment and does not resolve to Grade ≤ 2 within 21 days

- Non-immune-*mediated* adverse event that is considered to be treatment related and requires study treatment to be withheld for >21 days
- Immune-*mediated* adverse event that requires atezolizumab to be withheld for >42 days, unless approved by the Medical Monitor
- Any adverse event that meets criteria for permanent discontinuation per guidelines provided in Section 5.1
- Disease progression

Because of the potential for tumor flares with immunotherapies, resulting in early apparent radiographic progression (pseudoprogression/tumor immune infiltration), including the appearance of new lesions followed by delayed response (Wolchok et al. 2009), patients whose CT scans at the end of Cycle 2 meet criteria for disease progression may continue to receive study treatment at the discretion of the investigator and following discussion with the Medical Monitor, if certain criteria are met (see Section 3.1.4 for details). Cases of delayed pseudoprogression have also been described in patients with solid tumors treated with immunotherapies. In case of CT- findings suggestive for pseudoprogression in patients with persistent clinical benefit, the investigator should contact the Medical Monitor to discuss further patient management. Patients who continue to receive study treatment should have a CT scan repeated 4–8 weeks later.

- Pregnancy

In case of toxicity solely attributable to one drug of the combination requiring discontinuation, the other two drugs may be continued for patients experiencing clinical benefit as determined by the investigator after discussion with the Medical Monitor.

The primary reason for study treatment discontinuation should be documented on the appropriate eCRF.

Patients who discontinue study treatment will not be replaced, except as outlined below:

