5.1.1.3 Neutropenia

Grade 3 or 4 neutropenia, including febrile neutropenia, has been reported with obinutuzumab administration. Neutropenia resolved spontaneously or with use of hematopoietic growth factors. Patients who experience Grade 3 or 4 neutropenia should be closely monitored until neutrophil values return to at least Grade 2. Cases of late-onset neutropenia (ANC < 1000 cells/ μ L occurring \geq 28 days after obinutuzumab treatment has been completed or stopped) or prolonged neutropenia (ANC < 1000 cells/ μ L that does not resolve after 28 days without obinutuzumab treatment) have also been reported. The use of G-CSF is allowed for the treatment of neutropenia per institutional guidelines in this study. Prophylactic treatment with antibiotics should be administered as per standard practice. Guidelines for primary prophylaxis with G-CSF are provided in Section 4.3.2.6.

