5.1.3.5 Severe Skin Reactions

Angioedema and serious dermatologic reactions including Stevens-Johnson syndrome and toxic epidermal necrolysis have been reported during treatment with lenalidomide. These events can be fatal. Guidelines for the management of severe skin reactions are presented in [Table 10](#). Patients with a history of erythema multiforme, Grade ≥ 3 rash, or blistering following prior treatment with immunomodulatory derivatives (such as thalidomide and lenalidomide) will not be enrolled in the study.

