	Grade 1–2 ^c	
 • Continue study treatment. • Administer corticosteroids, NSAIDs, and/or narcotic analgesics at investigator's discretion.

Table 11 Guidelines for Management of Non-Hematologic Toxicities (cont.)

Event		Action to Be Taken
Dermatologic toxicity: Grade ≥ 2	Grade 3 with blistering or Grade 4	
 Permanently discontinue study treatment.
	Grade 2 or Grade 3 without blistering	
First occurrence:
 
 Withhold study treatment and evaluate patient at least every 7 days. Investigate etiology. Consult with a dermatologist. Topical corticosteroids may be required. If immune etiology is suspected, consider oral prednisone 10 mg or equivalent. If event is unresolved after 48–72 hours, administer oral prednisone 60 mg or equivalent. If there is improvement to Grade ≤ 1, resume obinutuzumab at full dose and resume lenalidomide at a reduced dose^a per guidelines in Section 5.1.5 for current and subsequent cycles. Atezolizumab may be resumed at full dose if the event is resolved and systemic corticosteroids dose is ≤ 10 mg/day of oral prednisone or equivalent. Contact Medical Monitor before resuming atezolizumab. 
Second occurrence:
 
 Permanently discontinue study treatment.
Hypothyroidism		
 Investigate etiology. Consult with an endocrinologist (refer to the Appendix 10 for guidance if immune etiology is suspected). Start thyroid replacement hormone. Monitor TSH weekly. 
Asymptomatic elevation of TSH
 
 Continue study treatment. 
Symptomatic elevation of TSH
 
 Withhold study treatment. If symptoms are controlled and TSH levels are decreasing, resume obinutuzumab and atezolizumab at full dose and lenalidomide at current dose. Permanently discontinue atezolizumab for Grade ≥ 3 hypothyroidism.

Table 11 Guidelines for Management of Non-Hematologic Toxicities (cont.)

Event	Action to Be Taken

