5.1.5.2 Toxicities during Maintenance Treatment

Table 12 provides guidelines for management of toxicities that occur during maintenance treatment.

Table 12 Guidelines for Management of Toxicities That Occur during Maintenance Treatment

Event	Action To Be Taken
Hematologic toxicity: Grade 3 or 4	For all patients: 
• Atezolizumab may be continued at the discretion of the investigator.• Withhold obinutuzumab and lenalidomide.• Administer G-CSF for neutropenia per institutional guidelines.• Administer RBCs or platelets as required.• If there is improvement to Grade ≤ 2, resume obinutuzumab and lenalidomide at same dose.• If study treatment is withheld for > 42 days, permanently discontinue study treatment.
Non-hematologic toxicity: Grade ≥ 2	For atezolizumab-related toxicities with possible immune etiology: 
• Follow guidelines presented in Table 11 for the management of atezolizumab-related toxicities with possible immune etiology (i.e., autoimmune colitis, hepatitis, pancreatitis, hypothyroidism, pneumopathy, skin, toxicity, or ocular toxicity). For all other non-hematologic toxicities: 
• Withhold study treatment.• If there is improvement to Grade ≤ 1 or baseline, administer study treatment at full dose.• If study treatment is withheld for > 42 days, permanently discontinue study treatment.

G-CSF = granulocyte colony-stimulating factor.

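### For maintenance, Table 12 and Section 4.6.2 conflict on how long treatment may be held and on life-threatening events, and no text says which prevails

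*Combined protocol and SAP*

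**What the plan says.** **Table 12, Section 5.1.5.2 (maintenance).** The non-hematologic row is labelled "Non-hematologic toxicity: Grade ≥ 2" and has no upper grade. Atezolizumab-related toxicities with a possible immune cause are sent to Table 11. The remainder come under "For all other non-hematologic toxicities": withhold study treatment; on improvement to Grade 1 or lower "or baseline, administer study treatment at full dose"; discontinue permanently if the hold exceeds 42 days. The hematologic row (Grade 3 or 4) withholds obinutuzumab and lenalidomide and lets the investigator continue atezolizumab. It resumes the two drugs at the same dose on improvement to Grade 2 or lower, and has the same 42-day limit.

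**Section 4.6.2 (no phase restriction).** Its list for permanent discontinuation of study treatment includes:
- anaphylaxis, acute respiratory distress or a Grade 4 infusion-related reaction;
- "Life-threatening adverse event";
- a related non-immune event of Grade 3 or higher that is not at Grade 2 or lower within 21 days;
- a non-immune "adverse event that is considered to be treatment related and requires study treatment to be withheld for >21 days";
- any event meeting a discontinuation criterion in Section 5.1.

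The 42-day figure in Section 4.6.2 applies only to immune-mediated events that hold atezolizumab.

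**Section 5.1.5** refers maximum delays to the tables that follow it and sends maintenance to Section 5.1.5.2.

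**The concern.** The two passages address the same maintenance patient and can lead to opposite actions: re-exposure to the full regimen, or permanent discontinuation. After a life-threatening event that is a patient-safety matter. With about 15 sites planned, practice could also differ according to which section a site consulted. Maintenance exposure, discontinuations for toxicity and the later adverse-event profile would then partly reflect that choice rather than the regimen.

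**Working it through.** The plan has no figure to reproduce. The check sets the two passages against the same events.

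**Inputs.** Table 12: resume after recovery, stop if held more than 42 days. Section 4.6.2: stop if a related non-immune hold exceeds 21 days, or if a related non-immune event of Grade 3 or higher is not at Grade 2 or lower within 21 days, or if the event is life-threatening, anaphylaxis or a Grade 4 infusion reaction. Days are counted from onset, with the hold assumed to start at onset; neither passage defines the count.

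**Band of disagreement on hold length.** 42 − 21 = 21 days, that is, holds of 22 to 42 days.

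| Event in maintenance | Table 12 | Section 4.6.2 | Agree? |
|---|---|---|---|
| Related, non-immune, non-hematologic, not life-threatening; Grade 1 by day 21 | Full dose | No stop criterion met | Yes |
| Same, Grade 1 first reached on day 30 | Full dose | Permanent stop | **No** |
| Same, still held on day 43 | Permanent stop | Permanent stop | Yes |
| Unrelated, not life-threatening; Grade 1 on day 30 | Full dose | No stop criterion met | Yes |
| Related Grade 3 neutropenia, Grade 2 first reached on day 30, atezolizumab continued | Resume obinutuzumab and lenalidomide at same dose | Permanent stop (Grade ≥3 rule) | **No** |
| Life-threatening event, anaphylaxis or Grade 4 infusion reaction in the residual row; recovered within 42 days | Full dose | Permanent stop | **No** |

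**Hematologic events.** Section 2 defines study treatment as the combination of all components. If atezolizumab continues, the 21-day hold rule is not clearly met. The clash that remains certain is with the rule on Grade 3 or higher at 21 days, which turns on time to resolution.

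**Severity.** Table 13 defines Grade 4 as life-threatening consequences or a need for urgent intervention. The conflict under the life-threatening rule therefore concerns life-threatening events, not all Grade 4 events. Anaphylaxis and infusion reactions are not in Table 12's list of events sent to Table 11, so they fall in the residual row. Section 4.3.2.2 (life-threatening atezolizumab infusion reaction) and Section 5.1.1.1 (suspected hypersensitivity to obinutuzumab) also carry stop instructions that Table 12 does not mention.

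**Precedence.** Section 5.1.5 points to the tables for delay limits but does not say that they replace Section 4.6.2. Section 4.6.2 treats the Section 5.1 criteria as one further item beside its own 21-day and life-threatening items.

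**The case against.** Two readings would remove much of the conflict.

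First, the specific text may govern. Section 5.1.5 refers delay limits to the tables, and Table 11, introduced as induction guidance, repeats the two 21-day rules. One could conclude that 21 days belongs to induction and 42 to maintenance. That reading is available for the hold limit, but Section 4.6.2 states its rules without a phase limit. It also does nothing for life-threatening events.

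Second, the passages may be cumulative: Section 4.6.2 is the stop list and Table 12 manages the rest. That would settle the severity question, where Table 12 is silent rather than expressly contrary. It would also leave the 42-day limit without effect for related non-immune holds beyond 21 days. No text adopts this reading either.

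Section 4.6.2 lets the other two drugs continue when toxicity is solely attributable to one. This is discretionary, and it does not reconcile the passages, because Table 12's non-hematologic row resumes study treatment as a whole. For hematologic events the boundary is not purely between phases: in induction, Table 10 answers a hold of more than 21 days by stopping lenalidomide, while obinutuzumab may continue.

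A reader might infer more than the documents support:

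- **Lenalidomide skin reactions as the main example.** Section 5.1.3.5 says "Angioedema and serious dermatologic reactions including Stevens-Johnson syndrome and toxic epidermal necrolysis have been reported during treatment with lenalidomide", and Table 11 permanently stops treatment for "Grade 3 with blistering or Grade 4". However, Table 12 sends atezolizumab-related skin toxicity with a possible immune cause to Table 11. A blistering Grade 3 event is not by definition life-threatening. A difference between Tables 11 and 12 alone may simply be a difference between phases.
- **The protocol expects neutropenia holds of 22 to 42 days.** Section 5.1.1.3 describes prolonged neutropenia as one "that does not resolve after 28 days without obinutuzumab treatment". In maintenance obinutuzumab is given every 2 months, so 28 days without it can pass with no hold.
- **The conflict governs 80% of treatment.** With 28-day months, 24 × 28 = 672 days of maintenance and 6 × 28 = 168 of induction give 672/840 = 80%. This is planned treatment time, not events or patients. Lenalidomide is limited to 12 maintenance months: 12 × 28 = 336 days, or 336/840 = 40%.

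**Conclusion.** The contradiction is real in two respects. (a) For related non-immune events the maximum hold is 21 days in Section 4.6.2 and 42 in Table 12, a two-fold difference. The 21-day resolution rule for Grade 3 or higher adds a clash that reaches hematologic events even when atezolizumab continues. (b) Table 12's residual non-hematologic row has no upper grade and no exception for life-threatening events, anaphylaxis or Grade 4 infusion reactions, all of which Section 4.6.2 lists for permanent discontinuation.

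The conflict does not extend to unrelated, non-life-threatening events, to every Grade 4 event, or to events that Table 12 sends to Table 11. How many patients would be affected cannot be derived from the documents. The primary endpoint is assessed before maintenance, so its assessment is not touched; what is at stake is safety in maintenance and the exposure and discontinuation data.

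The conclusion assumes that Section 4.6.2 applies in both phases, as its wording suggests. Figures 2 and 3 in Section 4.3.2.1 were not readable; any stop instruction in them would be one more place to reconcile. No position is taken on which rule is clinically right.

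**What to change.** The sponsor's clinical team should reconcile Table 12 with Section 4.6.2 so that a site finds one hold limit and one instruction for life-threatening events in maintenance, or should add a sentence stating which passage prevails. The values are for that team to decide.

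In the same edit, they should check Table 11 for consistency with the outcome. They should also check the cross-reference in Section 5.1.3.5, which points to Table 10 for severe skin reactions although Table 10 covers hematologic toxicity and the dermatologic row is in Table 11.

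The cost is wording in one table and one section, plus a cross-reference, carried by a protocol amendment. It needs no new assessments, patients or analyses.

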5.2 SAFETY PARAMETERS AND DEFINITIONS

Safety assessments will consist of monitoring and recording adverse events, including serious adverse events and adverse events of special interest, performing protocol-specified safety laboratory assessments, measuring protocol-specified vital signs, and conducting other protocol-specified tests that are deemed critical to the safety evaluation of the study.

Certain types of events require immediate reporting to the Sponsor, as outlined in Section 5.4.

5.2.1 Adverse Events

According to the ICH guideline for GCP, an adverse event is any untoward medical occurrence in a clinical investigation subject administered a pharmaceutical product, regardless of causal attribution. An adverse event can therefore be any of the following:

- Any unfavorable and unintended sign (including an abnormal laboratory finding), symptom, or disease temporally associated with the use of a medicinal product, whether or not considered related to the medicinal product
- Any new disease or exacerbation of an existing disease (a worsening in the character, frequency, or severity of a known condition), except as described in Section [5.3.6.10](#)
- Recurrence of an intermittent medical condition (e.g., headache) not present at baseline
- Any deterioration in a laboratory value or other clinical test (e.g., ECG, X-ray) that is associated with symptoms or leads to a change in study treatment or concomitant treatment or discontinuation from study treatment
- Adverse events that are related to a protocol-mandated intervention, including those that occur prior to assignment of study treatment (e.g., screening invasive procedures such as biopsies)

5.2.2 Serious Adverse Events (Immediately Reportable to the Sponsor)

A serious adverse event is any adverse event that meets any of the following criteria:

- Is fatal (i.e., the adverse event actually causes or leads to death)
- Is life threatening (i.e., the adverse event, in the view of the investigator, places the patient at immediate risk of death)

This does not include any adverse event that had it occurred in a more severe form or was allowed to continue might have caused death.

- Requires or prolongs in-patient hospitalization (see Section [5.3.6.11](#))
- Results in persistent or significant disability/incapacity (i.e., the adverse event results in substantial disruption of the patient's ability to conduct normal life functions)
- Is a congenital anomaly/birth defect in a neonate/infant born to a mother exposed to study treatment
- Is a significant medical event in the investigator's judgment (e.g., may jeopardize the patient or may require medical/surgical intervention to prevent one of the outcomes listed above)

The terms "severe" and "serious" are not synonymous. Severity refers to the intensity of an adverse event (e.g., rated as mild, moderate, or severe, or according to NCI CTCAE v3.0; see Section [5.3.4](#)); the event itself may be of relatively minor medical significance (such as severe headache without any further findings).

Severity and seriousness need to be independently assessed for each adverse event recorded on the eCRF.

Serious adverse events are required to be reported by the investigator to the Sponsor immediately (i.e., no more than 24 hours after learning of the event; see Section 5.4.2 for reporting instructions).

SPMs should be also reported as Serious Adverse Events. This requirement includes any SPM, regardless of causal relationship to study treatment occurring at any time during the study, from the time of signing the informed consent form up to 3 years after the last dose of lenalidomide.

5.2.3 Adverse Events of Special Interest (Immediately Reportable to the Sponsor)

Adverse events of special interest are required to be reported by the investigator to the Sponsor immediately (i.e., no more than 24 hours after learning of the event; see Section 5.4.2 for reporting instructions). Adverse events of special interest for this study include the following:

- Cases of potential drug-induced liver injury that include an elevated ALT or AST in combination with either an elevated bilirubin or clinical jaundice, as defined by Hy's law (see Section 5.3.6.7)
- Suspected transmission of an infectious agent by the study treatment, as defined below:
 - Any organism, virus, or infectious particle (e.g., prion protein transmitting transmissible spongiform encephalopathy), pathogenic or non-pathogenic, is considered an infectious agent. A transmission of an infectious agent may be suspected from clinical symptoms or laboratory findings that indicate an infection in a patient exposed to a medicinal product. This term applies only when a contamination of any of the study treatment components is suspected.
- TLS of any grade, irrespective of causality
- Second malignancies

Adverse events of special interest to atezolizumab are as follows:

- Pneumonitis
- Colitis
- Endocrinopathies: diabetes mellitus, pancreatitis, adrenal insufficiency, hyperthyroidism, and hypophysitis
- Hepatitis, including AST or ALT > 10 x ULN
- Systemic lupus erythematosus
- Neurological disorders: Guillain-Barré syndrome, myasthenic syndrome or myasthenia gravis, and meningoencephalitis

- Events suggestive of hypersensitivity, infusion-related reactions, cytokine-release syndrome, influenza-like illness, *and* systemic inflammatory response syndrome
- Nephritis
- Ocular toxicities (e.g., uveitis, retinitis, *optic neuritis*)
- Myositis
- Myopathies, including rhabdomyolysis
- Grade ≥ 2 cardiac disorders (e.g., atrial fibrillation, myocarditis, pericarditis)
- Vasculitis

5.2.4 Selected Adverse Events

Adverse events of special interest are listed in Section 5.2.3. Selected adverse events in this study are defined as adverse events for which additional data collection or analyses will be performed. Selected adverse events do not require immediate reporting if they are not serious (except for TLS and second malignancies).

The following adverse events are considered selected adverse events:

- Thrombocytopenia, including acute thrombocytopenia (events occurring during and within 24 hours following obinutuzumab infusion)
- Hepatitis B reactivation
- Cardiac events
- IRRs
- All infections, including progressive multifocal leukoencephalopathy
- Neutropenia, including prolonged neutropenia (neutropenia < 1000 cells/ μL that does not resolve after 28 days without obinutuzumab treatment) and late-onset neutropenia (neutropenia < 1000 cells/ μL occurring ≥ 28 days after obinutuzumab treatment has been completed or stopped)
- GI perforation

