4.3.2.5 Maintenance Treatment with Atezolizumab, Obinutuzumab, and Lenalidomide (Atezo+G+Len)

Patients who achieve a CR, a PR, or stable disease at EOI are eligible for maintenance treatment with atezolizumab and obinutuzumab for 24 months and lenalidomide for 12 months, as outlined in [Table 5](#).

Lenalidomide will be given before other agents are administered on the same day. Obinutuzumab will be administered next, followed by a line flush (unless there is a central line with more than one line/port), after which atezolizumab will be administered.

Maintenance treatment should start 8 weeks (\pm 1 week) after Day 1 of Cycle 6 and will continue until disease progression or unacceptable toxicity for up to 24 months.

Table 5 Maintenance Treatment

Treatment	Dose	Route	Regimen (Months 1–24)
Lenalidomide	10 mg	PO	Days 1–21 of each month for a maximum of 12 months
Obinutuzumab	1000 mg	IV	Day 1 of every other month (i.e., every 2 months), starting with Month 1
Atezolizumab	840 mg	IV	Days 1 and 2 of each month

IV=intravenous; PO=by mouth.

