5.3.1 Adverse Event Reporting Period

Investigators will seek information on adverse events at each patient contact. All adverse events, whether reported by the patient or noted by study personnel, will be recorded in the patient's medical record and on the Adverse Event eCRF.

After informed consent has been obtained **but prior to initiation of study treatment**, only serious adverse events caused by a protocol-mandated intervention (e.g., invasive procedures such as biopsies, discontinuation of medications) should be reported (see Section 5.4.2 for instructions for reporting serious adverse events).

After initiation of study treatment, all adverse events will be reported until 35 days after the last dose of study treatment. After this period, the investigator should report any serious adverse events that are believed to be related to prior study treatment (see Section 5.6).

An exception is made for Grade 3–4 infections (related and unrelated to study treatment), which should be reported until up to 2 years after the last dose of study treatment; and for SPMs (related and unrelated), which should be reported as serious adverse events until up to 3 years after the last dose of lenalidomide.

Similarly, second malignancies (related and unrelated to study treatment) will be reported indefinitely (even if the study has been closed) for patients who received obinutuzumab (see Section 5.6).

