Appendix 1 Schedule of Assessments (cont.)

- ^q All women of childbearing potential will have two negative serum pregnancy test results prior to initiating treatment: at 10–14 days prior to Day 1 of Cycle 1 and within 24 hours prior to Day 1 of Cycle 1. Urine pregnancy tests are required after treatment initiation (including times of treatment interruption) as follows: every week during the first cycle and then every 4 weeks during treatment for women with regular menstrual cycles or every 2 weeks during treatment for women with irregular menstrual cycles, any time the patient misses her period or has unusual menstrual bleeding, at the time of treatment discontinuation, and at least 35 days after the last dose of study treatment. If a urine pregnancy test is positive, it must be confirmed by a serum pregnancy test.
- ^r Includes hepatitis B surface antigen, total hepatitis B core antibody, and hepatitis C virus antibody.
- ^s Perform at the same time as tumor assessments at 12, 18, and 24 months after initiation of induction treatment.
- ^t Perform every 3 months until disease progression, or the start of new anti-lymphoma treatment, whichever occurs first.
- ^u See [Appendix 2](#) for detailed PK collection schedule.
- ^v Includes circulating lymphoma cells and/or cell-free circulating tumor DNA.
- ^w Includes B-cell counts (CD19), T-cell counts (CD3, CD4, and CD8), and NK cell counts (CD16 and CD56).
- ^x Perform at the same time as tumor assessments at 12 and 18 months after initiation of induction treatment.
- ^y Requires separate patient consent for RCR participation. Not applicable for a site that has not been granted approval for RCR sampling.
- ^z Availability of adequate archival or freshly biopsied tumor tissue samples should be confirmed at screening (see Section 4.5.7 for details).
- ^{aa} A tumor biopsy sample will be collected prior to the start of Cycle 2 and at the time of progression unless no adequate tumor site is accessible.
- ^{bb} Includes any medication (e.g., prescription drugs, over-the-counter drugs, herbal or homeopathic remedies, nutritional supplements) used by a patient from 7 days prior to the screening period until the EOI or EOM visit, whichever occurs later.

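### Late-onset neutropenia is a selected adverse event, but non-serious cases are reportable only until 35 days after the last dose of any study drug, which truncates its incidence

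*Combined protocol and SAP*

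**What the plan says.** Section 5.2.4 places late-onset neutropenia under the selected events and defines it by an ANC below 1000 cells/µL arising at least "28 days after obinutuzumab treatment has been completed or stopped". Of the selected events as a class it says: "Selected adverse events in this study are defined as adverse events for which additional data collection or analyses will be performed". Section 6.5 commits to summarizing and listing selected events.

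Section 5.3.1 sets the general limit: "After initiation of study treatment, all adverse events will be reported until 35 days after the last dose of study treatment". Sections 5.4.2.2 and 5.6 and Appendix 1 footnote cc give the same limit. The exceptions are:

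- related serious events: "After this period, the investigator should report any serious adverse events that are believed to be related to prior study treatment";
- Grade 3–4 infections, "which should be reported until up to 2 years after the last dose of study treatment";
- second primary malignancies, for 3 years after lenalidomide and indefinitely for patients who received obinutuzumab.

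Neutropenia has no exception of its own. Section 5.3.6.3 says that a neutropenia accompanied by an infection is to be recorded as a separate event.

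**The concern.** The two clocks do not match. The definition starts 28 days after obinutuzumab, while the reporting period closes 35 days after the last dose of whichever study drug is given last. When the drugs end close together, little time is left in which a non-serious case can both meet the definition and be reportable.

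The protocol names late-onset neutropenia among the important obinutuzumab risks (Sections 1.2.2.2, 5.1.1 and 5.1.1.3), so a reader of the study report will look for its incidence. What they would find is an incidence over a short span that varies between patients. The 2 years of Grade 3–4 infection data would also lack a consistent record of non-serious neutropenia occurring alongside the infection.

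**Working it through.** The documents give no figure for the reportable span, so there is none to reproduce. It follows from the calendar.

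**Inputs**

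- Late-onset threshold: 28 days after the last obinutuzumab dose (Section 5.2.4).
- Reporting limit: 35 days after the last dose of any study drug (Section 5.3.1).
- Induction: 28-day cycles, obinutuzumab on Day 1 of Cycle 6, lenalidomide through Day 21 (Table 2).
- Maintenance: starts 8 weeks after Cycle 6 Day 1, 1 month = 28 days, atezolizumab on Days 1 and 2 of each month through Month 24 (Table 3).
- Obinutuzumab in maintenance: "Day 1 of every other month (i.e., every 2 months), starting with Month 1" (Table 5), so the last dose is Month 23 Day 1.

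**Formula**

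Let day 0 be the last obinutuzumab dose and L the day of the last dose of any study drug. Reporting closes at L + 35. The reportable span is (L + 35) − 28 = L + 7 days.

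**Study calendar for an on-schedule maintenance completer**

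- Cycle 6 Day 1: 1 + 5 × 28 = day 141.
- Maintenance start: 141 + 56 = day 197.
- Last obinutuzumab: 197 + 22 × 28 = day 813.
- Last atezolizumab: 197 + 23 × 28 + 1 = day 842.
- Reporting closes: 842 + 35 = day 877, which is 877 − 813 = 64 days after obinutuzumab.

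**Spans by how treatment ends**

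| Course | L | Reporting closes (L + 35) | Span (L + 7) |
|---|---|---|---|
| Maintenance completed | 29 | day 64 | 36 days |
| Induction completed, no maintenance | 20 | day 55 | 27 days |
| All drugs stop on an obinutuzumab day | 0 | day 35 | 7 days |
| Last obinutuzumab Month 11, atezolizumab to Month 24 Day 2 | 13 × 28 + 1 = 365 | day 400 | 372 days |
| Last obinutuzumab Month 1, atezolizumab to Month 24 Day 2 | 23 × 28 + 1 = 645 | day 680 | 652 days |

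The last two rows are possible because Section 4.6.2 and Table 11 allow the other two drugs to continue after one is stopped.

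**Scheduled counts inside the span**

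- Maintenance completer: the EOM count, 35 days after the last dose, falls nominally on day 64. The Month 24 Day 1 count falls between days 22 and 31 (visit window ±3 days, sample up to 72 hours earlier), so it lies on the 28-day boundary.
- Induction only: the EOI count is 6–8 weeks after Cycle 6 Day 1, that is days 42–56.
- Induction stopped early for an adverse event: Appendix 1 footnote c allows EOI assessments 4–8 weeks (28–56 days) after the last dose. A count taken on days 36–56 comes after the reporting limit, by up to 56 − 35 = 21 days.

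**Counts in post-treatment follow-up**

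By column position, the hematology row of Appendix 1 is marked through EOM and blank in both follow-up columns. Footnote n ties hematology timing to induction and maintenance. The 3-monthly follow-up instruction, "Perform every 3 months until disease progression, or the start of new anti-lymphoma treatment, whichever occurs first" (footnote t), is attached to immunoglobulins and lymphocyte immunophenotyping, and the latter counts B, T and NK cells, not neutrophils. Column positions in this appendix are not dependable in the text copy, however. The 6-monthly CT mark (footnote jj) belongs to follow-up but falls under EOM. If the two maintenance columns are merged for hematology, as they appear to be for immunoglobulins, its last mark could be a follow-up mark.

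**The case against.** The strongest points on the other side are these.

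- **Serious cases are not lost.** Related serious events remain reportable without limit, and under Section 5.2.2 seriousness covers hospitalization and any significant medical event. This stands. A reader might infer that reporting simply stops at day 35 and nothing is collected afterwards. Sections 5.3.1 and 5.6 contradict that.
- **Infections bring the neutropenia with them.** Section 5.3.6.3 calls for neutropenia and an accompanying infection to be recorded separately, and Grade 3–4 infections are collected for 2 years. This stands in part. It rules out the inference that neutropenia behind a late infection cannot be seen. But the protocol does not say whether that recording rule applies after day 35 to a non-serious neutropenia, which the reporting limit otherwise excludes.
- **No promise is broken.** Section 5.2.4 offers additional data collection or analyses, so analysis alone would meet it, and late-onset neutropenia is a subtype, not an endpoint. This is fair. The point is that the summary would be truncated.
- **Low counts may still appear in the laboratory displays** of Section 6.5 when a count is taken and recorded. True, but the selected-event summary would not include them.
- **A missing follow-up count is not proven.** A reader might take the blank cells as showing that no count is scheduled. Given the shifted rows, this cannot be asserted without the original page. The reporting gap does not depend on it: where a count exists but reporting has closed, a non-serious case still yields no adverse event record.

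**Conclusion.** The mismatch is real and is established from running text alone. Non-serious late-onset neutropenia is reportable for 36 days in maintenance completers and 27 days in patients who complete induction without maintenance. The span falls to about 7 days when all drugs stop on an obinutuzumab day and exceeds a year when only obinutuzumab stops early. The first two figures assume on-schedule dosing.

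The consequence is an underestimate. A reader might infer an incidence near zero by construction. The documents do not support that: related serious cases stay reportable, some patients have long spans with regular maintenance counts, and no distribution of onset times is given from which to compute the loss. Because the span differs so much by how treatment ends, a crude proportion would also mix patients with very unequal opportunity to be counted. Prolonged neutropenia is less exposed: a case already recorded is followed to resolution or stability under Section 5.5.1, unless the patient is lost to follow-up or withdraws consent.

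This is a worthwhile correction to safety data collection. It does not affect the primary efficacy analysis.

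**What to change.** 1. In Sections 5.3.1 and 5.6 and Appendix 1 footnote cc, add neutropenia meeting the late-onset or prolonged definitions of Section 5.2.4 to the extended-reporting exception, alongside Grade 3–4 infections. This also settles whether a non-serious neutropenia accompanying a late infection is to be recorded.
2. Check the original Appendix 1 table. If hematology is blank in post-treatment follow-up, add a blood count to the existing 3-monthly draw (footnote t).
3. If neither change is made, state the reportable span beside the incidence in the safety summary.

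The cost is a few extra adverse event entries and, if needed, a count from blood already drawn. The added counts would yield little for the last completers: Section 3.2 ends the study when all patients have completed or discontinued treatment, so those patients would have few or no 3-monthly visits. One count every 3 months can also miss a transient event. These changes concern data collection only and alter no treatment rule.
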